4.1. General Considerations

Statistical analysis of this study will be the responsibility of Lilly or its designees. Any change to the data analysis methods described in the protocol will require an amendment ONLY if it changes a principal feature of the protocol. Any other changes to the data analysis methods described in the protocol, and the justification for making the change, will be described in this SAP or the clinical study report. Additional exploratory analyses of data will be conducted as deemed appropriate.

Unless otherwise stated, the efficacy analyses will be conducted on either EAS1 or EAS2. For treatment regimen estimand, efficacy analysis set 1 (EAS1 see the definition in Section 4) will be used; for efficacy estimand, other secondary and tertiary efficacy measures will be analyzed using the data up to the intercurrent events (EAS2 see the definition in Section 5). The treatment comparison will be based on either 2-sided test or 95% CI.

Unless otherwise noted, the safety analyses will be conducted on the SS. Percentages will be calculated using the safety population as the denominator. For events that are sex-specific, the denominator and computation of the percentage will include only participants from the given sex.

Unless otherwise stated, CGM analyses will be conducted based on the CGM Primary Analyses Population.

For continuous measures, summary statistics will include sample size, mean, SD, median, minimum, and maximum for both the actual and the change from baseline measurements. For certain variables that are considered to be log-normally distributed, the geometric mean and coefficient of variation (CV) will be provided instead. Either the mixed model repeated measurement (MMRM) model or the analysis of covariance (ANCOVA) model will be used to analyze continuous outcomes. Least-squares (LS) means and standard errors derived from the analysis models will also be displayed. Treatment comparisons will be displayed showing the treatment difference LS means and the 95% CIs for the treatment differences, along with the p-values for the treatment comparisons. For certain safety laboratory measures, log-transformed values will be analyzed in the statistical model instead. The actual change from baseline and percentage change from baseline will be presented using the derivation based on the output from the statistical model and the assumption of log-normality.

For categorical measures, summary statistics will include sample size, frequency, and percentages. Fisher's exact test or logistic regression will be used for treatment comparisons, unless otherwise stated. For laboratory values, both conventional (CN) and System International (SI) units will be presented. Therefore, both % and mmol/mol will be presented for HbA1c and both mg/dL and mmol/L will be presented for glucose measurements.

In this study, the negative binomial regression will be used to analyze the number of hypoglycemic episodes. Group Mean instead of LS mean will be estimated and delta method will be used to estimate the standard error of the Group Mean (Qu and Luo 2015). Group Mean is defined as the mean response in the treatment group for the studied population. The difference between LS mean and the Group Mean is that LS mean estimates the response by taking the

inverse link function on mean covariates, while the Group Mean takes the inverse link function on individual patient covariates first and then averages over all patients. For Level 2 hypoglycemia and severe hypoglycemia, the empirical method based on exposure adjusted rate (calculated by total number of events divided by total exposure) may be used for the treatment comparison if the number of episodes is too small and leads to convergency issues in the negative binomial regression model.

Below table describes the definition of baseline and post-baseline observations for different analyses.

Analysis	Baseline Observations	Post-Baseline Observations
HbA1c (treatment regimen estimand)	The baseline is the last non-missing assessment prior to or at the first day of study treatment.	Planned measurements at Visit 24 (secondary endpoint, Week 26) and Visit 31 (primary endpoint, Week 52) in EAS1. Use unplanned measurements if no planned measurement. Multiple imputation approach will be used to impute missing observations at Visit 24 (Week 26) and Visit 31 (Week 52).
HbA1c (efficacy estimand)	The baseline is the last non-missing assessment prior to or at the first day of study treatment.	Visit 5, 7, 15, 17, 24, 27, and 31 (Weeks 2, 4, 12, 16, 26, 36, and 52) in EAS2 for MMRM. Planned measurements at scheduled visits will be included. Use unplanned measurements if no planned measurements.
CGM parameters (treatment regimen estimand)	The baseline will be derived from the data collected during CGM session prior to the first dose date of study treatment. Multiple imputation will be used to impute missing observations at baseline.	The CGM session prior to Visit 24 (Week 26) and Visit 31 (Week 52) in EAS1 Multiple imputation approach will be used to impute missing observations at Visit 24 (Week 26) and Visit 31 (Week 52).
CGM parameters (efficacy estimand)	The baseline will be derived from the data collected during CGM session prior to the first dose date of study treatment.	The CGM sessions prior to Visit 7, 15, 24, and 31 (Weeks 4, 12, 26, and 52) in EAS2 for MMRM

Analysis	Baseline Observations	Post-Baseline Observations
Insulin dose during the treatment period	N/A	
All scheduled visits between Visit 3 and Visit 31 in EAS2 for MMRM.
 
The averages of weekly basal insulin doses between visits for individual participants will be used in the analysis. (Section 4.4.2.1)

Fasting glucose by SMBG	
The baseline period is the lead-in period up to the day of first dose of study treatment. Baseline will be derived as the average of all fasting glucose measurements between V2 date and the first dose date.
 
Multiple imputation will be used to impute missing observations at baseline for treatment regimen estimand.
	
All available data after the day of first dose of study treatment up to Week 52 (Visit 31) in EAS2 for MMRM (efficacy estimand).
 
Values at each visit will be derived as average of all fasting glucose measurements from the day post prior visit up to the day of next visit.
 
Data at Week 26 (Visit 24) and Week 52 (Visit 31) in EAS1 for ANCOVA with multiple imputation for missing data (treatment regimen estimand).

Fasting serum glucose	
The baseline is the last non-missing assessment prior to or on the day of the first dose of study treatment.
 
Multiple imputation will be used to impute missing observations at baseline for treatment regimen estimand.
	
All scheduled visits after the day of first dose up to Week 52 (Visit 31) in EAS2 for MMRM (efficacy estimand)
 
Planned measurements at scheduled visits will be included.
 
Data at Week 26 (Visit 24) and Week 52 (Visit 31) in EAS1 for ANCOVA with multiple imputation for missing data (treatment regimen estimand)
 
.

Analysis	Baseline Observations	Post-Baseline Observations
Participant-reported hypoglycemia	The baseline period is the lead-in period prior to the first dose date of study treatment.	
 Treatment period starts on the first dose date of study treatment and ends 
 At Week 52 (Visit 31) if completed treatment on the last dose date of study treatment + 10 days for LY3209590, +1 day for degludec if discontinued study treatment early Post-treatment period starts from 
 Week 52 (Visit 31) +1 day if completed treatment last dose date of treatment +11 days for LY3209590, +2 days for degludec if discontinued study treatment early and ends on the last date in the study
TEAEs	The baseline period includes the screening/lead-in period up to the first dose of study treatment (The AE Start Relative to Exposure Assessment CRF is used to determine).	Safety analysis period starts after the first dose and ends at the last visit in the study including safety follow-up period.
Safety laboratory tests, vital signs, and body weight	
The baseline will be the last non-missing assessment prior to or on the first dose date of study treatment
 
Planned measurements at scheduled visits will be included.
	
 All scheduled visits after the first dose date up to Visit 802 for MMRM or ANCOVA 
Planned measurements at scheduled visits will be included.

laboratory values elevated or low, vital signs and body weight categorical measures	
Starts from the screening visit and ends prior to or on the day of first dose of study treatment .
 
All available measurements at scheduled and unscheduled visits will be included. The baseline for weight will be the last non-missing value during the baseline period.
	
Starts after the day of first dose of study treatment and ends at the last visit in the study including both treatment period and follow-up period.
 
All available measurements at scheduled and unscheduled visits in the specified analysis period will be included.

Analysis	Baseline Observations	Post-Baseline Observations
Anti-LY3209590 antibody	Refer to PSAP	Refer to PSAP
Patient-reported outcomes	The baseline will be the data collected at Visit 3	
 • All scheduled visits after Visit 3 • Last collection after Visit 3

Abbreviation: ANCOVA = analysis of covariance; CGM = continuous glucose monitoring; CRF = case report form; EAS1 = efficacy analysis set 1; EAS2 = efficacy analysis set 2; MMRM = mixed model repeated measurement; N/A = not applicable; TEAE = treatment-emergent adverse event.

All analyses will be implemented using SAS Enterprise Guide Version 7.1 or above.

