2.3.3. Overall Benefit Risk Conclusion

Considering the clinical data to date and measures taken to minimize risk for the participants in this study, the potential risks identified in association with LY3209590 are justified by the anticipated benefits that may be afforded to insulin naïve participants with T2D.

3. Objectives, Endpoints, and Estimands

Objectives	Endpoints
Primary	
Demonstrate noninferiority of LY3209590 compared to insulin degludec for the treatment of T2D in adults	Change in HbA1c from baseline to Week 52
Key Secondary (Multiplicity Adjusted)	
Demonstrate noninferiority of LY3209590 compared to insulin degludec for participants using GLP-1 receptor agonists	Change in HbA1c from baseline to Week 52
Demonstrate noninferiority of LY3209590 compared to insulin degludec for participants not using GLP-1 receptor agonists	Change in HbA1c from baseline to Week 52
Demonstrate superiority of LY3209590 compared to insulin degludec in selected parameters of glycemic control	
 Change in HbA1c from baseline to Week 52 Time in glucose range between 70 and 180 mg/dL (3.9 and 10.0 mmol/L), inclusive, collected during the CGM session prior to Week 52
Other Secondary	
Compare the effect of LY3209590 to insulin degludec in parameters of glycemic control	
 Change from baseline to Week 26 of HbA1c Time in glucose range between 70 and 180 mg/dL (3.9 and 10.0 mmol/L), inclusive, collected during the CGM session prior to Week 26 Change from baseline to Weeks 26 and 52 of fasting glucose measured by SMBG Glucose variability measured during the CGM session prior to Weeks 26 and 52 Insulin dose at Weeks 26 and 52

Compare the effect of LY3209590 to insulin degludec on safety endpoints	
 Incidence and rate of composite of Level 2 and 3 hypoglycemia events during the treatment period Incidence and rate of composite of Level 2 and 3 nocturnal hypoglycemia events during the treatment period Change from baseline to Weeks 26 and 52 in body weight Measurements collected during CGM sessions prior to Weeks 12, 26, and 52 of 
 Time in hypoglycemia with glucose <70 mg/dL (3.9 mmol/L) Time in hypoglycemia with glucose <54 mg/dL (3.0 mmol/L) Time in hyperglycemia defined as glucose >180 mg/dL (10.0 mmol/L)

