7.1. Discontinuation of Study Intervention

When necessary, a participant may be **permanently discontinued** from study intervention. If so, the participant will remain in the study and follow procedures for remaining study visits, as shown in the SoA.

Participants who stop the study intervention permanently may receive another glucose-lowering medication. The new glucose-lowering medication will be recorded on the CRF for antihyperglycemic medications.

A participant should be **permanently discontinued** from study intervention if

- the participant becomes pregnant during the study
- the participant requests to discontinue study intervention
- the participant is diagnosed with an active or untreated malignancy, except for successfully treated basal or squamous cell carcinoma
- the participant did not take insulin degludec for more than 21 consecutive days or missed more than 3 consecutive doses of LY3209590 at any time during the study, or
- in the opinion of the investigator, the participant should permanently discontinue the study intervention for safety reasons.

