9.3.3.2. Other Secondary Endpoints

Other secondary endpoints include various measures for efficacy, safety, and patient-reported outcome questionnaires.

Efficacy measures and patient-reported questionnaires will be analyzed using the EAS2 unless otherwise noted.

Safety measures will be analyzed using the SS regardless of treatment discontinuation and use of rescue medications.

Analysis details will be provided in the SAP.

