1.2. Study Design

- This is a Phase 3, parallel-design, open-label, randomized control study to evaluate the efficacy and safety of LY3209590 administered once-weekly compared to insulin degludec administered daily.
- The study includes a 3-week screening and lead-in period, a 52-week treatment period, and a safety follow-up period approximately 5 weeks after the last visit in the treatment period.
- Assignment to treatment groups will be determined by an interactive web-response system (IWRS). Participants will be randomly assigned to 1 of the 2 treatment groups in 1:1 ratio (LY3209590: insulin degludec) at Visit 3 (Week 0). The number of participants in each subpopulation of participants using or not using GLP-1 RA will be approximately 50% of the study population with balanced treatment assignment. Stratification will be by country, HbA1c stratum at Visit 1 (Week -3) (<8.0%, ≥8.0%), sulfonylurea use at randomization, and GLP-1 RA use at randomization, regardless of oral or injectable administration.
- Rescue therapy will be considered during the treatment period if the participants meet the protocol criteria of severe, persistent hyperglycemia.
- If study intervention is permanently discontinued, the participant will be encouraged to continue participation in the study for continued monitoring. Both efficacy (including HbA1c) and safety data will continue to be collected per the schedule of activities in the protocol.
- Participants will collect blinded CGM for 2 weeks prior to Visit 3 (Week 0), for 4 weeks prior to Visit 7 (Week 4), Visit 15 (Week 12), Visit 24 (Week 26), Visit 31 (Week 52), and for 4 weeks after Visit 31 (Week 52). Dexcom G6 system provides readings every 5 minutes. In China, instead of the Dexcom G6 system, the Libre Freestyle H system which provides readings every 15 minutes will be used. Main analyses for CGM measurements will be conducted based on data from the Dexcom G6 system.

2. Statistical Hypotheses

Primary Hypothesis

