Type 1 error control strategy for primary and key secondary efficacy endpoints.

3. Analysis Sets

The following analysis populations and data sets are defined for the purpose of analysis.

Analysis Populations/ Data Sets	Description
Entered Population	All participants who sign the informed consent form.
Randomized Population	All randomized participants. Participants will be analyzed according to the treatment they were assigned.
Modified Intent-to-Treat (mITT) Population	All randomized participants who took at least 1 dose of study treatment. Participants will be analyzed according to the treatment they were assigned.
Efficacy Analysis Set 1 (EAS1) for treatment regimen estimand on efficacy measures	
The data will include:
 
 • mITT Population excluding participants discontinuing the study treatment due to inadvertent enrollment; and • all measurements regardless of the use of study treatment or rescue medications.
Efficacy Analysis Set 2 (EAS2) for efficacy estimand on efficacy measures	
The data will include:
 
 • mITT Population excluding participants discontinuing the study treatment due to inadvertent enrollment; and • measurement up to the early discontinuation of study treatment or the initiation of rescue medication. 
The data cutoff for participants who had intercurrent events is defined by the earliest date from below dates for individual participants except for the analysis on study dose:
 
 • the date of last study dose + 10 days for LY3209590, or +1 day for degludec; and • the start date of the first rescue medication. 
The data cutoff for analysis on study dose is defined by the earliest date from below dates for individual participants:
 
 • the date of last study dose; and • the start date of the first rescue medication
Safety Analysis Set (SS)	
The data will include:
 
 • mITT Population; and • all measurement regardless of the use of study treatment or rescue medications
Continuous Glucose Monitoring (CGM) Primary Analysis Population	All randomized participants who use Dexcom G6 system for CGM data collection.

4. Statistical Analyses

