4.9. Changes to Protocol-Planned Analyses

There are no changes but additional details are provided to the analyses described in the protocol.

5. Sample Size Determination

Approximately 888 participants will be randomly assigned to LY3209590 and insulin degludec in a 1:1 ratio. With the assumption of 15% dropout at Week 52, approximately 377 and 377 participants will complete 52 weeks of treatment on LY3209590 and insulin degludec, respectively.

The primary objective of this study is to test the hypothesis that LY3209590 is noninferior to insulin degludec on glycemic control as measured by change from baseline to Week 52 (Visit 31) in HbA1c in participants with T2D who are starting basal insulin for the first time. A total of 754 completers (377 on LY3209590 and 377 on insulin degludec) will provide an at least 99% statistical power to show noninferiority between LY3209590 and insulin degludec using the upper limit of a 2-sided 95% confidence interval (LY3209590 – insulin degludec) and these assumptions:

- a NIM of 0.4%,
- no true difference between treatment groups, and
- an SD of 1.1%.

This sample size also has at least 95% statistical power to show noninferiority between LY3209590 and insulin degludec using a 0.3% NIM at Week 52.

The number of participants in each subpopulation of background treatment will be approximately 50% of the study population with balanced treatment assignment to support the following secondary objectives, controlled for Type 1 error:

- To demonstrate noninferiority of LY3209590 to insulin degludec in HbA1c change from baseline to Week 52 for the subpopulation of participants using GLP-1 RAs; and
- To demonstrate noninferiority of LY3209590 to insulin degludec in HbA1c change from baseline to Week 52 for the subpopulation of participants not using GLP-1 RAs.

In each subpopulation, 188 completers for each study intervention will provide an approximately 90% statistical power to show noninferiority between LY3209590 and insulin degludec using the upper limit of a 2-sided 95% confidence interval (LY3209590 – insulin degludec) and these assumptions:

- a NIM of 0.4%,
- no true difference between treatment groups, and
- an SD of 1.1%.

The 754 completers will provide 95% statistical power to demonstrate the superiority of LY3209590 versus insulin degludec, of change in HbA1c from baseline to 52 weeks, assuming an SD of 1.1% and true mean difference is -0.3%, using the alpha of 0.05.

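### SAP 4.1 makes the Level 2/3 hypoglycemia endpoint an on-treatment count without declaring it, and pools two unlike groups in the post-treatment row

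*SAP*

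**What the plan says.** Protocol Section 3 lists as a secondary safety endpoint "Incidence and rate of composite of Level 2 and 3 hypoglycemia events during the treatment period", with a nocturnal counterpart. Protocol 4.1 describes a treatment period of 52 weeks. On the analysis, Protocol 9.3.3.2 states: "Safety measures will be analyzed using the SS regardless of treatment discontinuation and use of rescue medications". Protocol 9.2 and SAP Section 3 define the Safety Analysis Set alike, as the mITT population with "all measurement regardless of the use of study treatment or rescue medications".

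Participants who stop study drug are followed. Under Protocol 7.1 "the participant will remain in the study and follow procedures for remaining study visits", and SAP 1.2 says "Both efficacy (including HbA1c) and safety data will continue to be collected per the schedule of activities in the protocol".

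The participant-reported hypoglycemia row of the table in SAP 4.1 ends the treatment period at Week 52 for those who complete treatment. For the others it ends "on the last dose date of study treatment + 10 days for LY3209590, +1 day for degludec if discontinued study treatment early". What follows is a post-treatment period, which starts the next day "and ends on the last date in the study". On departures from the protocol, SAP 4.9 says: "There are no changes but additional details are provided to the analyses described in the protocol". SAP Section 1 likewise declares none.

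**The concern.** The protocol's rule, applied to a 52-week period, counts a discontinuer's events up to Week 52. The SAP's rule stops counting 10 days or 1 day after the last dose. The endpoint therefore has different numerators and person-time under the two documents, and a reader who relies on SAP 4.9 would not know it.

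The cut also falls at an awkward time for a weekly insulin. Protocol 6.8.4 gives a half-life of about 17 days and warns of hypoglycemia when a new daily insulin overlaps with residual LY3209590. For someone who switches early, most of that overlap comes after day 10, so it is reported in the post-treatment row. That row also holds every completer's washout, and the two groups have very different time at risk. A washout signal in completers could be diluted there.

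**Working it through.** **Text comparison.** The protocol applies a last-dose cutoff in one place, Section 9.3.1, for EAS2 efficacy data (+10 days, both arms). It applies none to safety data. In the SAP 4.1 table, the rows for adverse events, laboratory tests, vital signs and weight run on into follow-up without a last-dose cut. Hypoglycemia is the only one of these safety rows that has one, and its +10/+1 days are the EAS2 values in SAP Section 3.

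**Inputs from the documents.** 888 randomized 1:1, so 444 per arm; 377 completers per arm (888 × 0.85 / 2 = 377.4, which reproduces the stated 377); 444 − 377 = 67 non-completers per arm; a 52-week period of 364 days; last visit at Week 57; half-life 17 days.

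**Assumptions (none is given in the documents).** f, the share of the 67 who stop drug but stay in the study: 0.25 to 1. w, the week of last dose: 13 to 39. c, the event rate in the removed time relative to the on-treatment rate: 0.5 to 3. The middle case is f = 0.5, w = 26. The 15% behind the 67 is dropout, so it is only a proxy for discontinuers who are followed.

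**Residual drug at the cut.** 2^(−10/17) = 66.5% of the level at the last dose.

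**Days removed per discontinuer.** LY3209590: 364 − 7w − 10 = 263, 172 and 81 for w = 13, 26 and 39. Degludec: 364 − 7w − 1 = 272, 181 and 90.

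**Share of 0-52-week person-time removed, LY3209590.** s = 67·f·cut / (377·364 + 67·(7w + 10) + 67·f·cut).
- Middle case: 67 × 0.5 × 172 = 5,762 days (15.8 patient-years); 5,762 / (150,092 + 5,762) = 3.7%.
- Range: 0.9% (w = 39, f = 0.25) to 10.9% (w = 13, f = 1).
- The same formula for degludec (tail of 1 day) gives 3.9% in the middle case.

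**Single-arm rate shift.** The through-Week-52 rate divided by the SAP rate is 1 + s(c − 1). For LY3209590 the shift is −1.8% to +7.4% in the middle case and −5.5% to +21.8% at the widest.

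**Between-arm rate ratio.** With the same c in both arms the ratio changes by the factor [1 + s_LY(c − 1)] / [1 + s_deg(c − 1)].
- Middle case, c = 3: (1 + 2 × 0.0370) / (1 + 2 × 0.0390) = 0.996, or −0.4%. With c = 0.5 it is +0.1%.
- Over all combinations the change stays between −0.7% and +0.2%.
- If c were 3 for LY3209590 and 1 for degludec, the denominator would be 1 and the ratio would move by the full single-arm shift, +7.4% in the middle case.

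**Post-treatment row, LY3209590.** Days per discontinuer are 7(57 − w) − 10 = 298, 207 and 116 for w = 13, 26 and 39. A completer has 7 × 5 = 35. The discontinuers' share is 67·f·days / (67·f·days + 377·35).
- Middle case: 6,934.5 / (6,934.5 + 13,195) = 34.4%. Range: 12.8% to 60.2%.
- Suppose the rate ratio is 2.0 in completers' washout and 1.0 in the rest, both assumed. Weighted by this person-time, the pooled row would show 2.0 × 0.656 + 1.0 × 0.344 = 1.66, with a range of 1.40 to 1.87.

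**The case against.** The best defence is that the protocol leaves room for an on-treatment window. The endpoint is limited to the treatment period, Protocol 9.3.5 expresses its hypoglycemia windows in weeks of treatment, and the protocol defers analysis details to the SAP. The window was fixed before database lock, and an on-treatment count is a legitimate safety analysis. All of that stands, so the choice of main window is a trade-off. It does not remove the discrepancy: the protocol says discontinuation is disregarded, and the SAP reports no change.

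A reader might infer three stronger things that the documents do not support.
- **That events after the cut are lost.** They are not. SAP 4.6.3.1.1 plans post-treatment rates and incidences for each level. Severe events must also be recorded as serious adverse events, and the adverse-event period runs to the last visit. Persistent-recurrent hypoglycemia is assessed to the end of the study (SAP 4.6.2.1.2). Rescue does not trigger the cut.
- **That this rule causes the incidence model's lack of an exposure term.** A logistic model without exposure treats anyone who leaves early without an event as event-free under any window, including a window to Week 52 or study exit. It is a separate matter. The non-responder rule in SAP 4.5.2 serves tertiary efficacy composites and is not a fair comparison.
- **That the treatment comparison is distorted.** The +21.8% is a shift within one arm. It needs all 67 to stop at Week 13, all to stay, and a threefold rate.

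A window to Week 52 has its own asymmetry. It counts early switchers' residual-insulin events as treatment-period events, while completers' washout events stay outside.

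**Conclusion.** The discrepancy is real and its numerical effect is probably small. SAP 4.1 narrows the protocol's rule for a named secondary safety endpoint, and SAP Sections 1 and 4.9 do not say so. Under the assumed retention and timing, 0.9% to 10.9% of LY3209590 0-52-week person-time moves out of the window. The between-arm rate ratio changes by less than 1% unless off-treatment rates differ by arm, and the documents give no basis for assuming that they do or do not. The pooling in the post-treatment row is the larger practical weakness, because discontinuers could supply 12.8% to 60.2% of its LY3209590 person-time. The endpoint is outside the multiplicity scheme and the primary HbA1c analysis is untouched. This is an optional, low-cost improvement to the safety tables.

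**What to change.** - Keep the last-dose window as the main analysis if preferred, but label it on-treatment and list it with its reason as a change in SAP 4.9. Align the statement in SAP Section 1.
- Add incidence and rate of Level 2/3 hypoglycemia, all documented and nocturnal, from first dose to Week 52 or study exit if earlier, regardless of treatment discontinuation. SAP 4.7.1 already uses two windows for immunogenicity, so the layout has a precedent.
- Report the post-treatment row separately for completers (from the day after Week 52 to Visit 802) and early discontinuers, with person-time for each.

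The cost is a line in SAP 4.9 and some extra table rows. The data are already collected and no participants are added. The through-Week-52 version will include events that occur on non-study glucose-lowering drugs, so it should be read beside the on-treatment version.
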